| FACT-L | X | X | | 
The FACT-L will be administered on Day 1 for the first 3 Cycles (Cycle 1 Day 1, W6 and W12). Thereafter it will be administered every 2 Cycles (Weeks 24, 36, 48, etc).
 
On the day of study visits that include FACT-L assessment, the assessment will be performed PRIOR to any study procedures and treatment. Section 9.10
 |
| Pharmacokinetic (PK) and Immunogenicity Assessments | | | | |
| PK Samples | Throughout the study | | | Section 9.5.1 |
| Immunogenicity Samples | Throughout the study | | | Section 9.5.1 |
| | | | | |
| Clinical Drug Supplies | | | | |
| IRT Vial Assignment | X | X | X | Section 7.2 . Within 3 business days prior to dosing |
| Nivolumab 240 mg ^{b,c} | X | X | X | Section 7.1^c |
| Ipilimumab 1 mg/kg ^c | X | X | | Section 7.1^c |

- ^a If a dose is delayed, the procedures scheduled for that same time point should be delayed to coincide with when the time point's dosing actually occur (except radiographic tumor assessments).
- ^b Continues until disease progression, discontinuation due to unacceptable toxicity, 24 months of treatment, withdrawal of consent, or study closure.
- ^c Dosing window: nivolumab \pm 5 days unless dose frequency is less than 12 days and ipilimumab \pm 5 days unless dose frequency is less than 37 days)

Table 2-3: Follow-up and Survival Procedures (CA209817) - All participants

| Procedure | Follow-Up Visits 1 & 2 ^a | Survival Follow-up Visits ^b | Notes |
|---|-------------------------------------|--|---|
| Safety Assessments | | | |
| Targeted Physical Examination | X | | Section 9.4.1. To assess for potential late emergent study drug related issues. |
| Vital Signs | X | | Section 9.4 |
| Adverse Event Assessment | X | | Section 9.2. SAEs should be approved within 5 days from entry. Beyond 100 days from the last dose of study drug, participants will be followed for ongoing drug-related adverse events until resolved, return to baseline or deemed irreversible, or until lost to follow-up, withdrawal of study consent, or start of subsequent therapy. |
| Review of Concomitant Medications | X | | |
| Laboratory Tests | X | | Section 9.4.2. Required at Visit 1. Repeat at Visit 2 only if study drug related toxicity persists. |
| Pregnancy Test (WOCBP only) | X | | Section 9.2.5 |
| Patient Reported Outcomes | | | |

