| FACT-L | X | X | For participants who have discontinued study therapy, but continue to be followed for radiographic progression per Section 9.1.1, the FACT-L must be collected at each visit. On the day of study visits that include FACT-L assessment, the assessment will be performed PRIOR to any study procedures and treatment. FACT-L assessments may be administered in office or over the telephone. Section 9.10 |

Table 2-3: Follow-up and Survival Procedures (CA209817) - All participants

| Procedure | Follow-Up Visits 1 & 2 ^a | Survival Follow-up Visits ^b | Notes |
|---|-------------------------------------|--|---|
| Efficacy Assessments | | | |
| Radiographic Tumor Assessment (CT chest and known sites of disease. Repeat CT/MRI of abdomen with or without pelvis is required for participants with metastases in those areas at baseline, or if clinically indicated.) | X | X* | Section 9.1.1. For participants who discontinue study treatment for reasons other than progressive disease, follow up scans should be performed every 6 weeks (± 1 wk) up to Week 48, then every 12 weeks until progressive disease, initiation of subsequent systemic therapy, lost to follow-up, or withdrawal of consent. *Radiographic assessments for participants who have not experienced progressive disease must be obtained every 6 weeks (± 7 days), and not delayed until follow-up visits 1 & 2. |
| Collection of Survival Status and Subsequent Therapy Information | X | X | Collect every 3 months in Survival Visits until death, lost to follow-up, or withdrawal of study consent. May be performed by phone contact or office visit. Additional subsequent cancer therapy details such as regimen, setting of the regimen, line of therapy, start date and end date of each regimen, best response to the regimen and date of progression after second line therapy will be collected. |

^a Follow-Up Visit 1 to occur 35 days from the last dose (± 7 days) or coinciding with the date of discontinuation of study drug (± 7 days) if the date of discontinuation is greater than 42 days from the last dose. Follow-Up Visit 2 to occur 80 days from Follow-Up Visit 1 (± 7 days) . Patients should be monitored continuously (at least up to 100 days after the last dose) as an adverse reaction with nivolumab or nivolumab in combination with ipilimumab may occur at any time during or after discontinuation of therapy.

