4 OBJECTIVES AND ENDPOINTS

Table 4-1: Objectives and Endpoints

| Objectives | Endpoints |
|--|--|
| 
Primary
 
 To characterize the safety of nivolumab administered as a flat dose in combination with weight-based ipilimumab dosing in Cohorts A, B, and C. | 
 The primary objective of the study will be assessed by summarizing the number and percentage of participants who experience high grade (Grade 3-4 and Grade 5) treatment-related select and immune-mediated adverse events (imAEs) in Cohorts A, B, and C, analyzed separately. The select AEs of interest are the following: pneumonitis, interstitial nephritis, diarrhea/colitis, hepatitis, rash, endocrinopathies, and hypersensitivity/infusion reaction events. |
| Secondary | |
| 
 To assess progression-free survival (PFS), overall survival (OS), duration of response (DOR) of nivolumab administered as a flat dose in combination with weight-based ipilimumab dosing in Cohorts A, B, and C. | 
 PFS defined as the time from first dosing date to the date of the first documented tumor progression, as determined by investigators (per Response Evaluation Criteria in Solid Tumors [RECIST] v1.1), or death due to any cause, whichever occurs first. OS defined as the time from first dosing date to the date of death. |

Table 4-1: Objectives and Endpoints

| Objectives | Endpoints |
|---|---|
| | 
 DOR defined as the time between the date of first confirmed response to the date of the first documented tumor progression (per RECIST 1.1), or death due to any cause, whichever occurs first |
| 
 To assess the objective response rate (ORR) in Cohorts A, B, and C. | 
 ORR is defined as the number and percentage of participants with a best overall response (BOR) of confirmed complete response (CR) or partial response (PR). Best overall response (BOR) is defined as the best response designation, recorded between the date of first dose and the date of the initial objectively documented tumor progression per RECIST v1.1 or the date of subsequent therapy, whichever occurs first. |

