9.2 Adverse Events

The definitions of an AE or serious adverse event (SAE) can be found in [Appendix 3](#).

AEs will be reported by the participant (or, when appropriate, by a caregiver, surrogate, or the participant's legally authorized representative).

The investigator and any designees are responsible for detecting, documenting, and reporting events that meet the definition of an AE or SAE and remain responsible for following up AEs that are serious, considered related to the study treatment or the study, or that caused the participant to discontinue before completing the study.

Contacts for SAE reporting specified in Appendix 3

Immune-mediated adverse events are AEs consistent with an immune-mediated mechanism or immune-mediated component for which non-inflammatory etiologies (eg, infection or tumor progression) have been ruled out. IMAEs can include events with an alternate etiology which were exacerbated by the induction of autoimmunity. Information supporting the assessment will be collected on the participant's case report form.

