10.3.2 Safety Analyses

The primary safety analysis is scheduled to occur once all patients have initiated study therapy and have been followed for at least 3 months.

| Endpoint | Statistical Analysis Methods |
|--------------------------------|--|
| Primary in Cohorts A, B, and C | 
The number and percentage of participants who experience high grade (Grade 3-4 and Grade 5) treatment related select and immune-mediated adverse events (imAEs) will be summarized for all treated participants. High grade (Grade 3-4 and Grade 5) treatment related select AEs and imAEs will be tabulated using worst grade per NCI CTCAE v4 criteria by system organ class and Medical Dictionary for Regulatory Affairs (MedDRA) preferred term. The analysis is scheduled to occur once all patients have initiated study therapy and have been followed for at least 3 months.
 
The (select AEs consist of a list of preferred terms grouped by specific category (eg, pulmonary events, gastrointestinal events categories, etc). AEs that may differ from or be more severe than AEs caused by non-immunotherapies and AEs whose early recognition and management may mitigate severe toxicity are included as select AEs. The select AEs and the categories are defined by the Sponsor and the list that is the most current at the time of analysis will be used. Changes may be made to this list with each new version of MedDRA prior to database lock. Only select AEs occurring within 30 days of the last dose are included in the analysis.
 
Immune-mediated AEs are specific events (or groups of preferred terms [PTs] describing specific events) that include pneumonitis, diarrhea/colitis, hepatitis,
 |

| Endpoint | Statistical Analysis Methods |
|-------------|--|
| | nephritis/renal dysfunction, rash, and endocrine (adrenal insufficiency, hypothyroidism/thyroiditis, hyperthyroidism, diabetes mellitus, and hypophysitis). IMAE analyses included events, regardless of causality, occurring within 100 days of the last dose. These analyses will be limited to participants who received immunosuppressive medication for treatment of the event, with the exception of endocrine events (hypothyroidism/thyroiditis, hyperthyroidism, hypophysitis, diabetes mellitus, adrenal insufficiency), which were included in the analysis regardless of treatment since these events are often managed without immunosuppression. |
| Exploratory | Will be described in the statistical analysis plan finalized before database lock |

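### The immune-mediated part of the primary safety endpoint runs to 100 days after the last dose, whatever the cause, with no cut or flag at subsequent anti-cancer therapy, so immune-type events that begin on a next regimen can enter it

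*Combined protocol and SAP*

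**What the plan says.** The objectives table in Section 4 gives the primary endpoint as the number and percentage of participants with high-grade events: "Grade 3-4 and Grade 5) treatment-related select and immune-mediated adverse events (imAEs) in Cohorts A, B, and C, analyzed separately". Section 10.3.2 repeats this wording and then gives the two parts different counting rules.

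- **Select AEs:** "Only select AEs occurring within 30 days of the last dose are included in the analysis".
- **imAEs:** "IMAE analyses included events, regardless of causality, occurring within 100 days of the last dose". The list covers pneumonitis, diarrhea/colitis, hepatitis, nephritis or renal dysfunction, rash and named endocrine events. A treatment filter follows: "These analyses will be limited to participants who received immunosuppressive medication for treatment of the event, with the exception of endocrine events".

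Section 9.2 supplies the case definition: "Immune-mediated adverse events are AEs consistent with an immune-mediated mechanism or immune-mediated component for which non-inflammatory etiologies" have been ruled out, with infection and tumor progression as the examples. It also admits events of another etiology that induced autoimmunity made worse.

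Subsequent therapy appears in one AE rule only, the Adverse Event Assessment row of Table 2-3. Beyond day 100, ongoing drug-related events are followed until they resolve, return to baseline or are deemed irreversible, "or until lost to follow-up, withdrawal of study consent, or start of subsequent therapy". The same table collects the details of each later regimen, including "line of therapy, start date and end date of each regimen".

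**The concern.** The primary objective is to characterise the safety of one regimen. The imAE count ignores cause and stays open for 100 days, and many participants will stop treatment because of progression and move to another drug. If the next drug starts inside the window and a listed high-grade event follows, the event meets the imAE rule as written and is reported under flat-dose nivolumab plus ipilimumab.

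There is no comparator arm in which such events would cancel. The error can only raise the count, so a larger sample would not remove it. The next regimen and the speed of switching may also differ between the first-line cohorts (A and C) and the second-line cohort (B), so the effect need not be equal across cohorts. A reader of the planned table could not tell which events began after another anti-cancer drug was started.

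**Working it through.** **1. Is there a cut or a flag anywhere?**

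| Rule | Where | Effect of subsequent therapy |
|---|---|---|
| imAE count, to day 100, any cause | 10.3.2 | none stated |
| Select AE count, to day 30, treatment-related | 10.3.2 | none stated |
| AE and SAE collection, to day 100 | 9.2.1, 9.2.4 | none stated |
| Follow-up of ongoing drug-related AEs, beyond day 100 | Table 2-3 | follow-up ends |
| BOR | 10.3.1 | ends at subsequent therapy |
| PFS, DOR | 10.3.1 | censored at the last evaluable assessment before it (for DOR, before or on its start date) |
| OS | 10.3.1 | none stated |

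Events on a next regimen are therefore collected to day 100, and no rule separates them. The imAE window is 100 - 30 = 70 days longer than the select AE window, and the imAE rule has no causality filter.

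**2. Do the imAE filters remove them?**

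- *Event list:* toxicity outside the named types is not counted.
- *Immunosuppression:* non-endocrine events count only if immunosuppressive medication was given for them. Endocrine events are exempt.
- *Case definition (9.2):* non-inflammatory causes must be ruled out. This removes much ordinary chemotherapy toxicity. Another drug is not named among those causes, and an immune event caused by a later agent is not non-inflammatory.

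A steroid-treated pneumonitis or colitis on a later immune-active drug, or a listed endocrine event on any later drug, can pass all three.

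**3. Scale.** The plan states no figure to reproduce. The study is descriptive (3.1.1), part of Section 10.1 is redacted, and no imAE rate is given. The following is illustrative.

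Inputs:
- N = 400 treated in each of Cohorts A and B, and 100 in Cohort C (Section 10.1).
- Assumed true high-grade rate of 5%, borrowed for scale from Section 10.1, where at most 5% is a per-category figure for treatment-related select AEs in the earlier phase 1 study. It is not an imAE rate.
- Assumed share *s* starting new therapy within 100 days: 10-40%.
- Assumed rate *r* of a qualifying event on that therapy: 0-10%.

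Formula: added participants = N × s × (1 - 0.05) × r. The factor 0.95 leaves out those who already have a qualifying event. Example: 400 × 0.20 × 0.95 × 0.05 = 3.8, which moves the rate from 20/400 = 5.0% to 23.8/400 = 5.95%.

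Added participants of 400, with the resulting rate:

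| s | r = 1% | r = 2% | r = 5% | r = 10% |
|---|---|---|---|---|
| 10% | 0.38 (5.10%) | 0.76 (5.19%) | 1.9 (5.48%) | 3.8 (5.95%) |
| 20% | 0.76 (5.19%) | 1.52 (5.38%) | 3.8 (5.95%) | 7.6 (6.90%) |
| 40% | 1.52 (5.38%) | 3.04 (5.76%) | 7.6 (6.90%) | 15.2 (8.80%) |

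At r = 0 nothing is added. The range is 0 to 15.2 participants, or 0 to 15.2/400 = 3.8 percentage points.

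For comparison, the exact (Clopper-Pearson) 95% interval for 20/400 is 3.1% to 7.6%, an upper half-width of 2.6 points. Only the extreme cell (40%, 10%) exceeds it. For Cohort C, 5/100 gives 1.6% to 11.3%, an upper half-width of 6.3 points, and the largest inflation is again 3.8 points.

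**The case against.** **A full 100-day window may be deliberate.** A footnote to Table 2-3 asks for monitoring to at least 100 days because reactions can appear after treatment ends, and an any-cause count is a defensible conservative choice for safety. This stands. It argues against replacing the headline count outright, since a cut drops true late imAEs and shortens observation most for early switchers. It does not argue against showing the two parts separately.

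**The imAE count is not alone in having no cut.** A reader might infer that every other endpoint stops at subsequent therapy. The documents do not support that: OS and the 30-day select AE count have no such rule, and the Table 2-3 rule applies only beyond day 100, to ongoing drug-related events. The imAE part is simply where the gap is widest.

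**Relatedness may be required after all.** Section 10.3.2 says that "treatment related select and immune-mediated adverse events (imAEs) will be summarized for all treated participants", which can be read as applying the relatedness requirement to imAEs as well. If so, investigator attribution would limit the problem. The any-cause sentence is the more specific one, but the conflict is real and must be settled.

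**The harm is modest and uncertain.** There is no formal hypothesis, cohorts are analyzed separately, and the earlier-study tables contain no imAE figure for comparison. Section 5.5.4 leans towards a different mechanism of action after progression, which makes a second checkpoint agent less likely. The median PFS figures in Section 5.5.5 (3.2 months in low-TMB and 7.2 months in high-TMB patients on the weight-based combination) make early switching plausible, but they do not measure time from last dose to next therapy, and Section 8.1.2 allows treatment beyond progression. All of this stands and keeps the point a low-cost improvement.

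**Conclusion.** The point holds in limited form. As written, Section 10.3.2 lets high-grade immune-type events that begin on a next regimen enter the primary safety summary, and nothing marks them.

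A stronger reading is tempting: that toxicity of the next regimen is, as a general matter, counted against this combination. The documents do not support it. Only listed event types count, non-endocrine events need immunosuppressive treatment, and Section 9.2 excludes non-inflammatory causes, so much ordinary next-regimen toxicity stays out.

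The direction of any bias is upward. Its size is unknown: the 0 to 3.8 points above rest wholly on assumed switching and event rates and a borrowed 5% base rate, and in all but the extreme cell the effect is smaller than the upper half-width of the interval at N = 400. The conclusion also assumes that the any-cause sentence governs imAEs and that no cut is specified elsewhere. The text available contains no separate SAP section that could be checked for one; Section 10.3.2 defers only exploratory safety endpoints to the SAP.

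**What to change.** In Section 10.3.2, and in the SAP to match:

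1. Report the high-grade imAE count for each cohort in two parts: onset before the start of any subsequent systemic anti-cancer therapy and within 100 days of the last dose; and onset on or after that start, up to day 100. Show the full 100-day total beside them.
2. Base the statement about this regimen's toxicity on the first part, read alongside the total.
3. State whether the treatment-related qualifier in the endpoint wording or the any-cause rule governs imAEs, and align the Synopsis, Section 4 and Section 10.3.2.

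Cost: a few sentences and one table split, using regimen start dates that Table 2-3 already collects. Some true late imAEs will fall in the second part, where they remain visible and still count in the total.

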10.2 Populations for Analyses

| Population | Description |
|--|---|
| Enrolled | All participants who signed informed consent and were registered in IVRS |
| Treated | All participants who take at least 1 dose of any study medication. |
| Primary NSCLC cohorts treated participants | All treated participants in Cohort A and B. This is the primary cohort for safety and efficacy analyses |
| Special population NSCLC | All treated participants in the special population cohort (A1). |

| Population | Description |
|-----------------------------|--|
| cohort treated participants | Exploratory analysis will be conducted by special populations. |
| PK | All treated participants with available serum time-concentration data. |
| Immunogenicity | All treated participants with available immunogenicity data. |

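### The imAE part of the primary safety result counts non-endocrine events only if immunosuppression was given, so untreated Grade 3-5 events are missing from the imAE percentage, and the denominator wording is unclear

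*Combined protocol and SAP*

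**What the plan says.** Table 4-1 (Section 4) assesses the primary objective by "summarizing the number and percentage of participants who experience high grade (Grade 3-4 and Grade 5) treatment-related select and immune-mediated adverse events", separately in Cohorts A, B and C. Section 10.3.2 repeats the endpoint and says that "immune-mediated adverse events (imAEs) will be summarized for all treated participants". Section 10.2 defines the treated population as "All participants who take at least 1 dose of any study medication".

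Section 9.2 defines the event by mechanism: "Immune-mediated adverse events are AEs consistent with an immune-mediated mechanism or immune-mediated component for which non-inflammatory etiologies" have been excluded. It adds that supporting information is collected on the case report form. It does not require that the event was treated in any particular way.

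The treatment condition appears later in the Section 10.3.2 row: "These analyses will be limited to participants who received immunosuppressive medication for treatment of the event, with the exception of endocrine events". The endocrine events are those "which were included in the analysis regardless of treatment since these events are often managed without immunosuppression". The other listed categories (pneumonitis, diarrhea/colitis, hepatitis, nephritis/renal dysfunction, rash) have no exemption, either by grade or for death.

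The two parts of the endpoint also use different windows and causality rules. Select AEs count up to 30 days after last dose and carry no immunosuppression condition. imAEs count up to 100 days. Their definition disregards causality, although the endpoint sentence attaches treatment-relatedness to both parts.

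**The concern.** Receiving immunosuppression comes after the event and depends on it: the participant must survive long enough, the event must be recognised as immune-mediated, and the site must choose that treatment. Making it a condition for counting changes the question from how many participants experienced a high-grade imAE to how many had one that was treated in a certain way. Any error in the count is towards fewer events. It matters most for Grade 5, where death can come before treatment and each event carries weight.

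The protocol recognises the problem for endocrine events, which it exempts because they are often managed without immunosuppression. The same reasoning applies to a death before treatment starts, or to an event managed by stopping study drug.

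The study is descriptive, with no formal hypothesis (Section 3.1.1) and no data monitoring committee (Section 5.1.2). The reported percentages are the primary result, so the counting rule decides what is concluded.

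**Working it through.** **Step 1: which untreated events are lost, and from where.** Take a Grade 3-5 non-endocrine event that fits the Section 9.2 definition but was not treated with immunosuppression.

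| Event | Counted as imAE (10.3.2)? | Counted as select AE (10.3.2)? |
|---|---|---|
| Treatment-related, on the select list, within 30 days of last dose | No | Yes |
| Treatment-related, days 31-100 | No | No |
| Not judged treatment-related, within 100 days | No | No |
| Not on the select list, within 100 days | No | No |

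All four rows are missing from the imAE percentage. The last three are missing from both parts of the primary endpoint. The third row is a loss only if the causality-free imAE definition governs. If the treatment-related wording of the endpoint sentence governs, such events were never in the endpoint. Section 9.2.1 collects adverse events for 100 days after last dose, so the days 31-100 events are recorded.

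**Step 2: size, for illustration only.** The visible text gives no precision or power figure for the imAE percentage, so there is no plan figure to reproduce.

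Inputs:
- N = 400 treated in Cohort A and in Cohort B, and 100 in Cohort C (Section 10.1).
- Category rate p = 5%. This is the upper end that Section 10.1 quotes per category for Grade 3-4 treatment-related *select* AEs in CA209012, where the every-6-weeks cohort had 39 participants. It is borrowed here for imAEs.
- Untreated share u: not in the documents. Assumed 10%, 20% and 30%.

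Reported events = N × p × (1 − u); reported rate = p × (1 − u). Intervals are exact Clopper-Pearson 95%.

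| u | Events of 400 | Rate | 95% CI |
|---|---|---|---|
| 0 | 20 | 5.0% | 3.1-7.6% |
| 10% | 18 | 4.5% | 2.7-7.0% |
| 20% | 16 | 4.0% | 2.3-6.4% |
| 30% | 14 | 3.5% | 1.9-5.8% |

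The shortfall is 0.5 to 1.5 percentage points, or 10% to 30% in relative terms, simply because the reported rate scales with 1 − u. All three reduced rates lie inside the interval for the full count. In Cohort C, 100 × 5% = 5 events; losing one gives 4/100 = 4.0% (1.1-9.9%).

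For fatal events, suppose 4 in 400, with 1 untreated (both assumed). The reported rate falls from 4/400 = 1.0% (0.3-2.5%) to 3/400 = 0.75% (0.2-2.2%).

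**Step 3: the denominator.** The row opens with all treated participants and later limits the analyses to participants who received medication. Read as a rule for what counts as a case, 16 counted events give 16/400 = 4.0%. Read as an analysis set, with an assumed 120 down to 40 immunosuppressed participants, the same events give 16/120 = 13% up to 16/40 = 40%. The second reading is the less natural one, but the sentence does not exclude it.

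**The case against.** **The events are mostly still in the primary endpoint.** Pneumonitis, diarrhea/colitis, hepatitis, interstitial nephritis and rash are also select AEs in Table 4-1. A related pneumonitis death within 30 days counts there as Grade 5. This stands. A reader might infer that such deaths vanish from the primary result, and the documents do not support that. They leave the imAE percentage, and leave both parts only in the circumstances of Step 1.

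**There is no population conflict.** A reader might infer that Section 10.3.2 contradicts its own all-treated population. The sentence refers to treatment of the particular event and exempts a category, which works as a case rule but hardly as an analysis set. It is compatible with an all-treated denominator. This also stands: the wording is ambiguous, not contradictory.

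**The condition has a purpose.** imAEs are counted to 100 days and, by their definition, whatever the attributed cause. Requiring immunosuppression screens out events that are probably not immune-mediated. Replacing it with the Section 9.2 judgement could fail in a rapid death, where other causes may not have been fully excluded. This is a good reason to keep the existing tabulation, but not a reason to show nothing beside it.

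**The size is hypothetical.** Appendix 8 calls corticosteroids a primary therapy for these events, so the untreated share at high grade may be small. CA209012 reported no treatment-related deaths. Both points are fair, and the figures above are illustrations only.

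**No cohort comparison is planned.** A reader might infer that site steroid practice would distort differences between Cohorts A, B and C. The cohorts are analyzed separately, no comparison is specified, and the management guidance is common to all, so the documents give little support for that worry.

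**Conclusion.** The point holds as a gap in what is reported. Followed as written, Section 10.3.2 leaves an untreated high-grade or fatal non-endocrine imAE out of the imAE percentage, although neither Table 4-1 nor Section 9.2 sets a treatment condition. The event is also absent from the select-AE part if it falls on days 31-100, is off the select list, or is not judged treatment-related (this last only if the causality-free definition governs).

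The direction is certain: the count can only be too low. The size is not known. The 4.5% to 3.5% range rests on a borrowed 5% category rate and an assumed untreated share of 10% to 30%, and no figure in the documents is shown to be wrong. The denominator wording should be settled before tables are programmed, although the natural reading is all treated participants. This is an inexpensive improvement to the primary safety reporting. It does not invalidate the primary result.

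**What to change.** In Section 10.3.2:

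1. State that the denominator for every imAE percentage is all treated participants in the cohort, and that immunosuppression is a condition on which events count (numerator) only.
2. Keep the existing tabulation of events treated with immunosuppression. Beside it, as part of the primary safety result, report all Grade 3-4 and Grade 5 events in the listed imAE categories within 100 days of last dose, whether or not immunosuppression was given, and show every Grade 5 event.

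The second row is defined by category, grade and time, so it does not need a Section 9.2 determination recorded for each untreated event. It uses adverse event data collected to 100 days (Section 9.2.1) and concomitant therapy already on the case report form (Section 7.7.1). The first row keeps the sponsor's current definition.

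The cost is a wording change and one extra row per imAE table. The added row may show a slightly higher rate and include some events of less certain immune origin, which a footnote can say.
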